
 Change in quality of life as assessed by SF-36 total score, physical component summary (PCS), and mental component summary (MCS) change from baseline to Weeks 16, 24, and 52 Fatigue as assessed by FACIT-F change from baseline to Weeks 16, 24, and 52 Proportion of subjects achieving ACR50 at Weeks 24 and 52 Proportion of subjects with resolution of enthesitis at Weeks 24 and 52 as assessed by LEI in subpopulation that had enthesitis (LEI >0) at baseline Proportion of subjects achieving an improvement in PsAID of at least 3 units at Weeks 24 and 52 compared to baseline in subjects with PsAID ≥ 3 at baseline Proportion of subjects achieving ACR20 at Weeks 24 and 52 Mean (median) ACR-N at Week 16, 24, and 52, where ACR-N is defined as the largest number N such that ACR-N is met (analogous to the primary endpoint definition of ACR 50) Change in enthesitis at Weeks 16, 24 and 52 as assessed by change from baseline in LEI Time to resolution of enthesitis at weeks 4, 12, 16, 24 and 52 among subjects with enthesitis (LEI > 0) at baseline Occurrence of enthesitis (LEI > 0) at weeks 4, 12, 16, 24 and 52 among subjects without enthesitis (LEI = 0) at baseline 	
 Change in SF-36 total score, PCS, and MCS at Weeks 16, 24, and 52 Change in FACIT-F at Weeks 16, 24 and 52 ACR50 at Weeks 24 and 52 Resolution of enthesitis (LEI = 0) at Weeks 24 and 52 PsAID response at Weeks 24 and 52 ACR20 at Weeks 24 and 52 ACR-N at Weeks 16, 24 and 52 LEI change from baseline to Weeks 16, 24 and 52 Time to resolution of enthesitis at weeks 4, 12 16, 24 and 52 among subjects with enthesitis (LEI > 0) at baseline Occurrence of enthesitis (LEI > 0) at week 4, 12, 16, 24 and 52 among subjects without enthesitis (LEI = 0) at baseline

Objectives	Endpoints

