### 2.5. Secondary Efficacy Variables

The secondary efficacy variables of the study are:

- PASI90 at Week 16 in subjects with  $\geq 3\%$  BSA psoriasis at baseline
- Resolution of enthesitis (LEI  $\geq 0$ ) at Week 16
- MDA at Week 16
- ACR20 at Week 16
- PsAID response at Week 16 in subjects with PsAID  $\geq 3$  at baseline
- HAQ-DI change from baseline to Week 16

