- Change from baseline in LEI at Week 16, 24, 52
- Time to resolution of enthesitis at weeks 4, 12 and 16 among subjects with enthesitis (LEI > 0) at baseline
- Occurrence of enthesitis (LEI > 0) at week 4, 12 and 16 among subjects without enthesitis (LEI = 0) at baseline
- HADS change from baseline to Weeks 16 and 52
- Decrease of at least 2 from baseline in LEI, among subjects with baseline LEI of at least 2, at weeks 4, 12 and 16
- Subject's Global Impression of Change Questionnaire at weeks 16 and 52
- AUC for ACR-N through week 16
- Time to first achievement of ACR50
- Time to first achievement of PASI90 among subjects with at least 3% BSA at baseline
- Time to first achievement of MDA
- Time to first achievement of ACR20
- Time to first achievement of PsAID improvement of at least 3 among subjects with PsAID at least 3 at baseline
- Time to first achievement of PASI100 among subjects with at least 3% BSA at baseline
- Trough plasma concentrations of izokibep at collected timepoints
- Presence of anti-drug antibodies (positive or negative)

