### **3.2.2. Population of Subjects Targeted by the Clinical Question**

The population of subjects is all randomized males and females  $\geq 18$  years and  $\leq 75$  years with active PsA ( $\geq 3$  SJC66 and  $\geq 3$  TJC68 at screening and baseline visits) as further defined by the inclusion and exclusion criteria.

For some of the secondary endpoints, further restrictions on inclusion in the analysis result in a smaller target population, a subset of the FAS:

- First secondary endpoint: achieving PASI90. This endpoint will be assessed in subjects with  $\geq 3\%$  BSA psoriasis at baseline, to allow for a calculation of PASI90.
- Second secondary endpoint: resolution of enthesitis. This endpoint will be assessed using only subjects with enthesitis at baseline ( $LEI > 0$ ), to ensure this represents improvement in enthesitis rather than having no enthesitis at baseline.
- Sixth secondary endpoint: proportion of subjects achieving an improvement in PsAID of at least 3 units. This endpoint will be assessed using only subjects with PsAID of at least 3 at baseline, to ensure subjects are capable of meeting endpoint, since negative values of PsAID are not possible.

As for the secondary endpoints, further restriction on inclusion in the analysis result in a smaller target population, a subset of the FAS:

- The exploratory endpoint: change from baseline in spine pain NRS. This endpoint will be assessed using only subjects with sacroiliitis at baseline.
- The exploratory endpoint: change from baseline in spine pain NRS. This endpoint will be assessed in those with investigator assessed spinal involvement.
- The exploratory endpoint: time to resolution of enthesitis. This endpoint will be assessed using only subjects with enthesitis at baseline ( $LEI > 0$ ), to ensure this represents improvement in enthesitis rather than having no enthesitis at baseline.
- The exploratory endpoint: occurrence of enthesitis. This endpoint will be assessed using only subjects with enthesitis at baseline ( $LEI = 0$ ), with occurrence defined as of enthesitis ( $LEI > 0$ ) summarized at weeks 4, 8, 12 and 16.

Other secondary and exploratory endpoints will be assessed using the full analysis set. The population being studied represents a population normally seen in clinical practice. This ensures the activity of izokibep can be evaluated across a distribution of disease severity in the study.

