## 5.2. Handling of Dropouts, Missing Data, and Outliers

### 5.2.1. Handling of Missing Efficacy Data

Tender (and swollen) joint count will be the sum of the joints where tenderness (or swelling) is marked as Present on the CRF. A missing response will be treated the same as an Absent response, in that, it will not contribute to the joint count.

Subjects with missing efficacy assessments will be imputed as non-responders (non-response imputation or NRI) for dichotomous endpoints. Subjects with a missing component of a composite endpoint will be imputed as non-responders for that component. The subject may therefore be a responder to the endpoint, if the subject met a sufficient number of criteria from other components.

Subjects missing one or more components of composite endpoints will be included, illustrated for the primary endpoint, ACR50, as follows:

Situation	ACR50 result
If both SJC66 and TJC68 have reductions $\geq 50\%$ : 
 
- If at least 3 of the other 5 components have reductions <math>\geq 50\%</math>, irrespective of missing/available on the others
 
- If at least 3 of the other 5 components have a reduction of <math>< 50\%</math>, irrespective of missing/available on the others
 
- All other situations
 
	
Responder
 
Non-responder
 
Missing

If result is available on both of SJC66 and TJC68, and at least one has $<50\%$ : 
 
- Irrespective of results or missingness on the other 5 components
 
	Non-responder
If one of SJC66 and TJC68 is missing, and the other has reduction $\geq 50\%$ : 
 
- If at least 3 of the other 5 components have reductions <math>\geq 50\%</math>, irrespective of missing/available on the others
 
- If at least 3 of the other 5 components have a reduction of <math>< 50\%</math>, irrespective of missing/available on the others
 
- All other situations
 
	
Missing
 
Non-responder
 
Missing

If one of SJC66 and TJC68 is missing, and the other has reduction $<50\%$ : 
 
- Irrespective of results or missingness on the other 5 components
 
	Non-responder

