### **6.6.5. Exploratory Analysis**

Exploratory endpoints will be analyzed analogously to primary and secondary endpoints, with the exception of a prespecified alpha-controlling testing strategy. Exploratory endpoints of dichotomous measurements will be analyzed analogously to primary endpoints. Exploratory endpoints of continuous measurements will be analyzed analogously to the secondary endpoint of change in physical function of HAQ-DI from baseline to Week 16. P-values for exploratory endpoints will be considered descriptive and not considered conclusive. A summary table of all primary, secondary and exploratory endpoints will be presented using point estimates only, to visually assess izokibep 160 mg dosed QW, izokibep 160 mg dosed Q2W, izokibep 80 mg dosed Q4W and placebo.

All primary, secondary and exploratory endpoints defined for comparing izokibep 160 mg QW or izokibep 160 mg Q2W to placebo will also be reported for comparing izokibep 80 mg Q4W to placebo.

Dose-response will be investigated through analyses of the primary and secondary endpoints, which will use all four treatment arms (izokibep 160 mg QW, izokibep 160 mg Q2W, izokibep 80 mg Q4W and placebo) in a single analysis for each endpoint. A p-value for the global test of the hypothesis that all groups have identical response rates will be reported for each endpoint, not subject to type I error rate control or any multiple comparison procedure. P-values will also be reported for all pairwise comparisons for each endpoint. Dose-response relationships will be assessed qualitatively from these analyses. Due to the error in dose sequence in the Q2W and Q4W arms, additional investigations will include assessment of endpoints that may be achieved earlier, including ACR20 and PASI75 at week 4 (at which time all subjects received correct dose sequencing).

The following binary endpoints before or on Week 16 will be analyzed analogously to the primary endpoints of ACR50 at Week 16. The number and proportion of subjects for binary

endpoints in each treatment group will be reported without strata along with Clopper-Pearson 95% CI. Common risk difference with Cochran-Mantel-Haenszel weighting will be used to calculate a 95% CI, and p-values from the stratified test will be reported as well. The binary endpoints after week 16 will include number and proportion along with Clopper-Pearson 95% CI without strata according to the four randomized treatment groups. No p-value will be reported.

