- ACR70 at Weeks 16, 24, and 52
- DAPSA  $\leq 14$  at Weeks 16, 24, and 52
- cDAPSA  $\leq 14$  at Weeks 16, 24, and 52
- DAPSA  $\leq 4$  at Weeks 16, 24, and 52
- cDAPSA  $\leq 4$  at Weeks 16, 24, and 52
- PASI75 at Weeks 16, 24, and 52
- PASI100 at Weeks 16, 24, and 52
- MDA at Weeks 24, and 52
- VLDA at Weeks 16, 24, and 52
- Resolution of dactylitis at Weeks 16, 24, and 52 among those with dactylitis at baseline
- ACR50 at Weeks 24 and 52
- PASI90 at Weeks 24 and 52 among those with  $\geq 3\%$  BSA psoriasis at baseline
- Resolution of enthesitis (LEI = 0) at Weeks 24 and 52 among those with LEI  $> 0$  at baseline
- Resolution of enthesitis (SPARCC = 0) at Weeks 24 and 52 among those with SPARCC  $> 0$  at baseline
- PsAID response at Weeks 24 and 52
- ACR20 at Weeks 24 and 52
- Occurrence of enthesitis (LEI  $> 0$ ) at weeks 4, 8, 12 and 16, among subjects with no enthesitis (LEI = 0) at baseline
- Decrease of at least 2 in LEI, among subjects with baseline LEI of at least 2, at weeks 4, 8, 12 and 16.

The following continuous endpoints will be analyzed at week 16 with an MMRM model as specified in sec 6.6.3, and after week 16 with standard summary statistics for continuous endpoints. LS mean changes and associated SEs with associated 95% CI and p-values will be presented. Models through week 16 will include all data up to Week 16. The following continuous endpoints after Week 16 will be analyzed according to the four randomized treatment groups. Mean changes and associated SEs along with 95% CI according to the four randomized treatment groups will be presented without strata. No p-values will be reported.

- Change from baseline in DAS28-CRP at Weeks 16, 24, and 52
- Change from baseline in DAPSA/cDAPSA at Weeks 16, 24, and 52
- Change from baseline in PASDAS at Weeks 16, 24, and 52

- Change from baseline in mNAPSI at Weeks 16, 24, and 52 in those with nail psoriasis at baseline
- Change from baseline in mTSS at Weeks 16 and 52
- Change from baseline in SPARCC enthesitis score at Weeks 16, 24, and 52 in those with enthesitis at baseline (SPARCC>0)
- Change from baseline in spinal pain NRS at Weeks 16, 24, and 52
- Change from baseline in spine pain NRS in those with sacroiliitis on pelvic x-ray
- Change from baseline in spine pain NRS in those with investigator assessed spinal involvement
- Correlation of investigator assessed spinal involvement with sacroiliitis on x-ray

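### Three enthesitis rules in the SAP need correcting: the LEI >= 0 threshold in 2.5, the Week 8 time point, and non-responder imputation for new enthesitis

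*SAP*

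**What the plan says.** **Resolution of enthesitis.** This is the second secondary endpoint and is tested within the alpha-controlled sequence. SAP 2.5 lists it as "Resolution of enthesitis (LEI $\geq 0$ ) at Week 16". The protocol (Section 3) and SAP 2.3 define resolution at Week 16 as LEI = 0, and SAP 2.6 and 6.6.5 use LEI = 0 for Weeks 24 and 52.

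**Time points.** SAP 6.6.5 requests occurrence of new enthesitis "at weeks 4, 8, 12 and 16, among subjects with no enthesitis (LEI = 0) at baseline", and also "Decrease of at least 2 in LEI, among subjects with baseline LEI of at least 2, at weeks 4, 8, 12 and 16". SAP 3.2.2 likewise has occurrence "summarized at weeks 4, 8, 12 and 16". SAP 2.6 instead has "Occurrence of enthesitis (LEI > 0) at week 4, 12 and 16 among subjects without enthesitis (LEI = 0) at baseline", and protocol Section 3 has "Occurrence of enthesitis (LEI > 0) at weeks 4, 12, 16, 24 and 52".

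**Missing data.** SAP 5.2.1 states: "Subjects with missing efficacy assessments will be imputed as non-responders (non-response imputation or NRI) for dichotomous endpoints". No exception is made for endpoints where the event is a bad outcome. SAP 6.6.5 introduces the list that contains occurrence of enthesitis with: "The following binary endpoints before or on Week 16 will be analyzed analogously to the primary endpoints of ACR50 at Week 16".

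**Baseline labels.** SAP 3.2.2 describes the occurrence population as having enthesitis at baseline but gives LEI = 0 in brackets. SAP 6.6.5 and 6.6.6 define time to resolution in subjects described as having enthesitis, again with LEI = 0 in brackets.

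**The concern.** Non-responder imputation is conservative when the event is favourable, because a missing subject is denied a success. New enthesitis is a failure. If the listed event is coded as the response, as it is for the other items in that list, a missing subject is credited with staying free of enthesitis. An arm that loses more subjects then looks better protected.

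A Week 8 analysis of an index that is not measured at Week 8 has no data. The threshold in SAP 2.5 cannot separate responders from non-responders. The endpoint it describes is third of 14 tests in the fixed sequence, so 11 later tests, including the whole Q2W family, depend on it.

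**Working it through.** **1. The plan's own figure.** SAP 2.3 gives 95% power for 25% versus 60% resolution with 50 per arm, two-sided 0.05. With pooled variance, the mean rate is 0.425.
- Null SE = sqrt(2 x 0.425 x 0.575 / 50) = 0.0989.
- Alternative SE = sqrt((0.25 x 0.75 + 0.60 x 0.40) / 50) = 0.0925.
- Power = Phi((0.35 - 1.96 x 0.0989) / 0.0925) = Phi(1.69) = 95.4%.
- With 30 per arm the same formula gives 79.9%, against the stated 80% or more.

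These figures rest on LEI = 0 and are not in dispute.

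**2. LEI >= 0 taken literally.** LEI runs from 0 to 6 (protocol 8.1.3.5), so every assessed subject qualifies. With missing subjects imputed as non-responders, the rate in each arm is 1 minus its missing share: 100%, 95% or 90% at 0%, 5% or 10% missing, in place of 25% versus 60%. The comparison would then measure only differential missingness.

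**3. Week 8.**

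| Source | Weeks up to 16 |
|---|---|
| Schedule of Activities, LEI row | Day 1, 4, 12, 16 (Week 8 cell blank) |
| SAP 5.1.4, efficacy visits | 2, 4, 12, 16 |
| SAP 2.2.3 and 2.6; protocol Section 3 | 4, 12, 16 |
| SAP 3.2.2 (occurrence) and 6.6.5 (occurrence, LEI decrease) | 4, 8, 12, 16 |

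Nominal Week 8 is Day 8 x 7 + 1 = 57, which SAP Table 2 assigns to the Week 12 window (Days 57 to 98). If imputation is nevertheless applied at Week 8, both endpoints show 0% in every arm. The risk difference is 0 and so is its standard error, so the SAP 6.6.1 statistic is 0/0.

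**4. Direction of imputation for occurrence.** Let q be the rate among assessed subjects and m the missing share.
- Missing = no event: reported rate = q(1 - m).
- Missing = event: reported rate = q(1 - m) + m.

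The documents give neither q nor m. Assume q = 20% in both arms, so there is no true effect:

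| Missing, arm A vs arm B | Missing = no event | Missing = event |
|---|---|---|
| 5% vs 15% | 19% vs 17% | 24% vs 32% |
| 10% vs 20% | 18% vs 16% | 28% vs 36% |
| 5% vs 25% | 19% vs 15% | 24% vs 40% |

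The false difference is q times the gap in missingness under the first rule, and (1 - q) times the gap, in the opposite direction, under the second. For a 10-point gap these are 2 and 8 points. The LEI = 0 subset is about 40 of 100 per arm if 60% have enthesitis, and about 70 if the cap on LEI = 0 is reached. Two points is then 0.02 x 40 = 0.8 to 0.02 x 70 = 1.4 subjects.

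**The case against.** The strongest reply is that none of this would change a conclusion of the trial.

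- **LEI >= 0.** A reader might infer that a confirmatory endpoint will be counted wrongly. The documents do not support that. The protocol and SAP 2.3 say LEI = 0, SAP 3.2.2 restricts the endpoint to subjects with LEI > 0 at baseline, and SAP 6.6 and 6.6.3 speak of resolution in those subjects. A programmer would have to overlook all of these. What stands is that the SAP's own list of secondary variables states a threshold that cannot be used.
- **Week 8.** A reader might expect false zeros with p-values attached. No p-value exists when estimate and standard error are both zero. Since SAP 5.1.4 analyses by the visits in the Schedule of Activities, an empty row is at least as likely. What stands is a request for an analysis without data.
- **Imputation.** A reader might conclude that the SAP expressly scores missing subjects as enthesitis-free. It does not: it says only non-responder, which for a bad event could be read as the unfavourable state. What stands is that the natural coding gives the favourable reading, and nothing in the text rules it out. The endpoint is exploratory, and SAP 6.6.5 treats its p-values as descriptive.
- **Worst-case imputation as the sole remedy.** It would not be a minor adjustment. In the example it moves 18% to 28% and 16% to 36%, and its false difference is four times as large. This part of the reply stands in full and shapes the fix.

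**Conclusion.** The point holds as a correction to SAP definitions and to one imputation rule. LEI >= 0 is an evident slip, but it sits in the definition of an alpha-controlled endpoint and should not remain. Week 8 contradicts the assessment schedule and can produce only an empty or all-zero row with an undefined test. For occurrence of enthesitis, the blanket rule under its natural coding understates the rate by the factor (1 - m) and favours the arm with more missing data. The size, 18% versus 16%, rests on an assumed 20% occurrence and assumed 10% and 20% missingness; the direction depends on the coding, not on those values. Imputation works as intended for resolution itself and for the LEI decrease, where the event is favourable. The primary endpoint and the stated power are unaffected.

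**What to change.** Amend the SAP as follows.

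- **2.5:** define resolution as LEI = 0 at Week 16 in subjects with LEI > 0 at baseline.
- **3.2.2 and 6.6.5:** delete Week 8 for occurrence of enthesitis, and in 6.6.5 also for the LEI decrease of at least 2.
- **5.2.1 and 6.6.5:** state that imputing missing as no event does not apply to occurrence of enthesitis. Report the observed-case rate together with a missing-as-occurrence analysis, and show the missing share by arm. Note that the second analysis raises rates markedly and is itself sensitive to unequal drop-out, so the two should be read as a pair.
- **Baseline labels:** in 3.2.2 describe the occurrence population as without enthesitis (LEI = 0); in 6.6.5 and 6.6.6 define time to resolution in subjects with LEI > 0.

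The cost is SAP wording and one extra exploratory table. No visit, assessment or sample size changes. Reported occurrence will be higher than under the present rule wherever data are missing, and considerably higher in the missing-as-occurrence analysis.

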### **5.2.2. Handling of Missing Safety Data**

In general, missing clinical laboratory data, vital signs, and ECG data will not be imputed. Adverse event imputations for missing severity or relationship are given in Section 6.7.2. Unknown or partial medication and AE date imputations are given below and are to be used only for the assessment of prior/concomitant status for medications and treatment-emergent status for AEs.

### **5.2.3. Handling of Missing Age and Partial and Missing Dates for Adverse Events, Prior/Concomitant Medications**

#### Missing Age at Time of Informed Consent

Where the age at time of informed consent is missing and year of birth is collected, the following convention will be used:

The day and month will be completed as 02JUL (the 183rd day of the year). For example, Date of Birth specified as -----1980 will be completed as 02JUL1980.

#### Missing or Partial Adverse Event and Prior/Concomitant Medication Start/Stop Dates

Missing and/or incomplete dates for medications and AEs are imputed in a manner resulting in the earliest onset or the longest duration during the Treatment Period, whilst ensuring that the start date does not occur after the stop date. The stop date will not be imputed if the medication or AE is “Ongoing”. Technically, this will be done as follows:

For a missing/incomplete start date/time the earliest date/time of the following will be imputed:

- The later date of: the earliest possible start date/time, and the date/time of the first dose of treatment.
- The latest possible start date/time.
- The latest possible stop date/time.

For a missing/incomplete stop date/time the later date/time of the following will be imputed:

- The earlier date/time of the latest possible stop date/time and the date/time of last dose of treatment.
- The earliest possible stop date/time.

- The earliest possible start date/time.

Here, the earliest possible date/time is defined as:

- The date/time itself if available.
- The date/time of the first day of the month at 00:00hrs, if month and year are available but the day/time is missing.
- The date/time of the first day of the year at 00:00hrs, if year is available but day/time and month are missing.
- 00:00hrs on the day of informed consent, if the date/time is completely missing.

The latest possible date/time is defined as:

- The date/time itself if available.
- The date/time of the last day of the month at 23:59hrs, if month and year are available but the day/time is missing.
- The date/time of the last day of the year at 23:59hrs, if year is available but day/time and month are missing.
- 23:59hrs on the date of last known date on the study for the subject plus one year, if the date/time is completely missing.

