## 5. Data Handling

### 5.1. Time Points and Visit Windows

#### 5.1.1. General Definitions

All assessment days will be related to the first day of the first dose of the study drug.

Day 1 is defined as the date of the first dose of the study drug. Relative days after Day 1 are calculated as (assessment date – Day 1 date) + 1. Relative days prior to Day 1 are calculated as (assessment date – Day 1 date). The day prior to Day 1 is Day -1. There is no Day 0.

The date of the first dose of study drug for each subject will be taken from the Study Drug Administration eCRF page. If the date in this eCRF page is missing, alternatively the date of enrollment/randomization will be used.

The date of the last dose of study drug for each subject will be taken from the Study Drug Administration form, with the last study drug administration date from any visit used as the date of last study drug.

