#### 5.1.3. Treatment Period

Data collected on Day 1 will be assigned to the Treatment Period unless the time (HH:MM) of data collection and time (HH:MM) of the first dose of study drug are both recorded and the data collection time is before the time of the first dose of study drug. In this case, the assessment will be assigned to the screening period. If the time (HH:MM) of data collection is not recorded but the protocol and/or eCRF includes an instruction to the effect that all Day 1 assessments are to be performed prior to the first dose of study drug, the data collected at Day 1 will be assigned to the screening period. However, adverse events and concomitant medications starting on Day 1, will be assigned to the Treatment Period, unless the time (HH:MM) demonstrates otherwise.

The Treatment Period is defined as the period from the date/time of the first dose of study drug to Week 52 (one week after the last dose) or early termination (end of treatment visit

should be completed within 14 days of withdrawal and follow-up visits should be completed at 8 weeks and 14 weeks after the last dose of study drug, where possible).

Treatment will be divided into two periods, Period 1 and Period 2, Period 1 will start at the first dose of study drug and ends at Week 16 when Week 16 assessments are completed and before administration of study drug. Period 2 will start at the time of administration of study drug at Week 16 and end at Week 52 or early termination/end of treatment visit.

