### 6.7.2. Adverse Events

All SAEs will be collected from the signing of the ICF until the 8-week follow-up visit. All AEs will be collected from the first dose of study drug until 4 weeks after the last dose of study drug. All AEs recorded on the eCRF will be coded using the latest MedDRA dictionary around the time of Database Lock and classified as either AEs or treatment-emergent AEs (TEAEs) as follows:

- TEAEs are either events with start date and time after the start of the Treatment Period and up to 4 weeks after the end of the Treatment Period, or events with start date and time prior to the start of the Treatment Period whose severity worsens on or after the start of the Treatment Period. TEAEs for period 2 are either events with start date and time after the start of administration of Week 16 treatment and up to 4 weeks after the end of the Treatment Period, or events with start date and time prior to the start of administration of Week 16 treatment whose severity worsens on or after the start of administration of Week 16 treatment. For subjects who receive treatment in period 2, TEAEs with start date after the start of period 2 will be assigned to period 2 only, not to period 1.
- Treatment-Emergent Serious AEs (TESAEs) will be defined as TEAEs which meet the criteria as Serious = “Yes”.
- The relationship between a TEAE and treatment is assessed as related or not related. A treatment-related TEAE will be defined as a TEAE considered by the investigator as related to treatment or with unknown/missing relationship to treatment.
- Assessment of AE severity will be based on eCRF AEs form.
- TEAEs leading to discontinuation of treatment are defined as TEAEs where “Action Taken with Study Treatment” is indicated as “Drug Withdrawn”.

In addition to the aforementioned AE types, the following TEAEs of special interest will be monitored:

- Candida infection,
- Inflammatory bowel disease,
- Suicidal ideation.
- Malignancies
- MACE (major adverse cardiovascular and cerebrovascular events: cerebrovascular accident and transient ischemic attack, non-fatal myocardial infarction or unstable angina, cardiovascular death)
- Tuberculosis (TB)
- Infections (serious, opportunistic, or fungal only)
- Cytopenias

- Systemic hypersensitivity reaction

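### Missing or partial AE start dates are floored only at the first dose, so in the placebo-to-izokibep group uncertain onsets around the Week 16 switch are booked to placebo

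*SAP*

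**What the plan says.** SAP 5.2.3 states that missing or incomplete AE dates are "imputed in a manner resulting in the earliest onset or the longest duration during the Treatment Period". The imputed start is the earliest of three dates. The first is given as "The later date of: the earliest possible start date/time, and the date/time of the first dose of treatment"; the other two are the latest possible start and the latest possible stop. The earliest possible start is defined case by case, for example "The date/time of the first day of the month at 00:00hrs, if month and year are available but the day/time is missing" and "00:00hrs on the day of informed consent, if the date/time is completely missing". SAP 5.1.1 fixes what the first dose is: "Day 1 is defined as the date of the first dose of the study drug". For Group 1 that dose is placebo.

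SAP 5.1.3 starts Period 2 at the Week 16 administration. Under SAP 6.7.2 an AE is treatment-emergent for Period 2 if it starts after that administration, or if its severity worsens on or after it. For subjects treated in Period 2, "TEAEs with start date after the start of period 2 will be assigned to period 2 only, not to period 1". SAP 6.7 tabulates Period 1 by randomized arm, so Group 1 appears there as placebo.

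For Day 1 alone, SAP 5.1.3 has a same-day rule: "adverse events and concomitant medications starting on Day 1, will be assigned to the Treatment Period, unless the time (HH:MM) demonstrates otherwise". SAP 5.2.2 says the date imputations "are to be used only for the assessment of prior/concomitant status for medications and treatment-emergent status for AEs".

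**The concern.** Imputing the earliest onset is cautious at Day 1, because it makes an uncertain event treatment-emergent. At Week 16 it works the other way in Group 1: the earlier the imputed start, the more likely a possible izokibep event is counted under placebo. Elsewhere SAP 6.7.2 resolves uncertainty against the drug: a missing relationship counts as related, and a missing severity counts as Grade 3, or Grade 5 if fatal.

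The protocol treats Week 16 much like a second first dose. The one-hour on-site observation at Weeks 0, 1 and 2 is repeated at Weeks 16, 17 and 18 (Protocol 6.1.1), and Protocol 9.3.5 asks for crossover subjects to be summarized separately before and after the switch.

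Two summaries are at stake: the Period 1 placebo column, which is the only concurrent placebo safety comparator, and the Period 2 summary of Group 1 after crossover, which loses the same events.

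**Working it through.** The plan states no figure to reproduce. The check applies the written rule literally.

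**Rule.** Imputed start = min{ max(earliest possible start, first dose), latest possible start, latest possible stop } (SAP 5.2.3). Period 2 if the imputed start is after the Week 16 dose, otherwise Period 1 (SAP 5.1.3 and 6.7.2).

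**Worked case, Group 1.** Assume a first (placebo) dose on 01 Feb 2023 at 10:00. The Week 16 dose is 112 days later, on 24 May 2023 at 10:00.

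| AE start as recorded | Imputed start | Period |
|---|---|---|
| May 2023, day missing | 01 May 2023 00:00 | 1 (placebo) |
| 2023 only | 01 Feb 2023 10:00 | 1 (placebo) |
| Nothing recorded | 01 Feb 2023 10:00 | 1 (placebo) |
| Nothing recorded, stop date 01 Dec 2023 | 01 Feb 2023 10:00 | 1 (placebo) |
| June 2023, day missing | 01 Jun 2023 00:00 | 2 |
| 24 May 2023, time missing | not defined; 00:00 would be before the dose | no rule |

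In the fourth row the stop date is more than six months after the switch and does not alter the assignment.

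**Month-only onset in the crossover month.** Over 365 possible first-dose dates, the event fell in Period 1 in 365 of 365. Assuming onset is uniform within that month, about 50% of such events truly start after the izokibep dose, ranging from 2% to 99% with the calendar day of the dose.

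**Completely missing onset.** All go to Period 1. Assuming onset is uniform over Weeks 0 to 52, the share truly after the switch is (52 − 16)/52 = 36/52 = 69%. Over Weeks 0 to 55 (AE collection runs to 4 weeks after the Week 51 dose) it is (55 − 16)/55 = 39/55 = 71%.

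**Effect on placebo incidence.** Group 1 has about 100 subjects, so each newly counted subject adds 1/100 = 1 percentage point. SAP 6.7.2 counts a subject once per preferred term, so a subject who already had the event on placebo adds nothing.

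**Effect on the Period 1 contrast.** Let p_A and p_P be the correct Period 1 incidences on izokibep and placebo, and m_A and m_P the fractions of subjects added to Period 1 by the imputation. The reported difference is (p_A + m_A) − (p_P + m_P) = (p_A − p_P) + (m_A − m_P). Every arm receives izokibep after Week 16 and the rule applies to all of them, so m_A is not zero. The contrast narrows only if m_P exceeds m_A, that is, by the excess due to first exposure in Group 1. What changes only in Group 1 is the treatment label: elsewhere a misplaced event is still an izokibep event.

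**The case against.** The strongest reply is that little is at stake. The first izokibep dose in Group 1 is given on site with at least one hour of observation, and site visits follow at Weeks 17 and 18, so onsets near that dose should be among the best recorded. Safety is descriptive and has no p-values (Protocol 9.3.5). AE listings show the original dates (SAP 6.7.2), so affected events stay visible. Events that worsen on or after the Week 16 dose still count in Period 2. On the uniform assumption, about half of the month-only onsets truly precede the dose. All of this stands, and it limits the size. It does not change what the rule does with the uncertain dates that do occur.

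A second reply is that the restriction in SAP 5.2.2 does not mention period assignment. However, SAP 6.7.2 defines Period 2 TEAEs as a treatment-emergent status, so the imputed start decides the period. On the narrower reading, uncertain events would have no period rule, which is also a gap.

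Three stronger readings are tempting, and the documents do not support them:

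- A reader might infer a shift of many points from the injection site reaction rates in Protocol 2.2.3.3 (38.9% and 61.9%). The first is drug-related reactions over a 52-week core period (42/108). The second comes from 21 subjects after single and multiple subcutaneous doses. Neither is a first-dose rate, and neither concerns missing dates. A 20-point shift would need uncertain onset at one dose in about half as many subjects as reacted over 52 weeks (20/38.9 = 51%).
- A reader might infer that untimed Week 16 onsets are sent to placebo by rule. SAP 5.2.3 does not list a known day with a missing time among its cases, so the assignment is undefined.
- A reader might infer that the Period 1 difference is biased by the full number of misassigned Group 1 events. The offset shown in the working contradicts this.

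**Conclusion.** The defect is real but limited. As written, the rule assigns to placebo every Group 1 AE whose start is completely missing, is known only to the crossover month, or is known only to a year that could span the switch, unless worsening severity also brings it into Period 2. It does so whether or not onset could have followed the first izokibep dose. The same events drop out of the post-crossover izokibep summary. Untimed onsets on the Week 16 date have no rule.

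The size is about 1 percentage point of placebo incidence per newly counted subject. The number of uncertain onsets is not in the documents and is probably small. The Period 1 contrast moves only by the excess of such events in Group 1 over the izokibep arms. The shares of 50% and 69% to 71% rest on uniform onset, which is an assumption. No hypothesis test is affected.

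**What to change.** Amend SAP 5.2.3 and 6.7.2, before unblinding, for Group 1 subjects who received the Week 16 dose:

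- If the earliest possible start is before the Week 16 dose, but neither the latest possible start nor the latest possible stop is, set onset to the time of that dose and assign the event to Period 2. The assignment must be explicit, because SAP 6.7.2 requires a start after the administration and an imputed start equal to it would be a tie.
- Assign AEs dated on the Week 16 day to Period 2 unless the recorded time shows onset before the dose, in line with the Day 1 rule.
- Keep the existing first-dose rule in the arms randomized to izokibep. Applying the new anchor to those roughly 225 subjects (100 + 100 + 25) would move uncertain events, including true early ones, out of the izokibep columns in the only controlled period, which is the anti-conservative direction.
- Report the number of AEs with imputed onset by arm and period.

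The cost is SAP wording, one derivation and one small table, with no change to data collection. Some true placebo events will move to izokibep, which is the conservative direction. Group 1 will also be handled differently from the other arms, and the table of imputed onsets lets a reader judge how much that matters.
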